9. STUDY TIMELINES

- *Describe the duration of an individual's participation in the study*
- *Describe the duration anticipated to enroll all study subjects*
- *The estimated date of study completion*

The duration of an individual's participation will last as long as it takes to perform their scheduled ultrasound testing. Ultrasound testing usually takes no more than 30 minutes. Enrolled subject's EMR will be reviewed for 6 months after they undergo the ultrasound testing. We anticipate it will take 6-8 months to enroll all study subjects.

10. ENDPOINTS

- *Describe the primary and secondary study endpoints*
- *Describe any primary or secondary safety endpoints*

The primary endpoint of the study will be the treatment outcomes for the patients. We will review readmission rates (30 days from the day of the ultrasound) as well as compliance to first follow-up appointment after the ultrasound of interventional cohort. These endpoints will be compared to those of a historical cohort of persons who were treated for similar pathologies in the past.

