7. ELIGIBILITY CRITERIA

- *Describe the characteristics of the subject population, including their anticipated number, age, ranges, sex, ethnic background, and health status. Identify the criteria for inclusion or exclusion of any subpopulation.*
- *Explain the rationale for the involvement of special classes of subjects, such as fetuses, pregnant women, children, prisoners or other institutionalized individuals, or*

others who are likely to be vulnerable. You cannot include these populations in your research, unless you indicate such in the protocol

- *Similarly, detail exclusionary criteria: age limits, special populations (minors, pregnant women, decisionally impaired), use of concomitant medications, subjects with other diseases, severity of illness, etc.*

INTERVENTIONAL COHORT:

Inclusion:

- Age 18 years of age or older
- Suspected vascular insufficiency that requires ultrasound evaluation
- Subject is able to sign a consent form
- Scheduled ultrasound testing at the wound center to evaluate vasculature

Exclusion:

- Younger than 18 years old
- Subject is not scheduled to have ultrasound testing at the wound center
- Subject is unable to or refuses to consent to participate

RETROPECTIVE COHORT:

Inclusion:

- Age 18 years of age or older
- Subjects who have undergone vascular ultrasound testing at the wound center
- Ultrasound tests performed from 1/1/2019-12/31/2019
- Subjects who were followed by the wound center team after undergoing ultrasound testing for vascular insufficiency

Exclusion:

- Younger than 18 years old
- Subjects who underwent testing outside the above mentioned timeframe
- Subjects who were not followed by the wound center team after undergoing ultrasound testing for vascular insufficiency

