8. NUMBER OF SUBJECTS

- *Indicate the total number of subjects to be accrued locally. If applicable, distinguish between the number of subjects who are expected to be pre-screened, enrolled (consent obtained), randomized and complete the research procedures.*
- *If your study includes different cohorts, include the total number of subjects in each cohort.*
- *If this is multisite study, include total number of subjects across all sites.*

The total number of subjects we plan to enroll is 270. We plan to enroll 135 subjects into the 3D imaging cohort of this study. Another 135 patients will be identified retrospectively for the historical cohort.

The sample size calculation was based on the primary outcome of 30-day readmission. We assumed a readmission rate of 10% in the 2D group and a readmission rate of 2% in the 3D group. We would need 135 patients in each group to have 80% and a confidence level of 95% to detect this difference.

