20. PROVISIONS TO PROTECT PRIVACY INTERESTS OF SUBJECTS

- *Describe the methods used to identify potential research subjects, obtain consent and gather information about subjects to ensure that their privacy is not invaded.*
- *In addition consider privacy protections that may be needed due to communications with subjects (such as phone messages or mail).*

Potential research subjects will be identified from the patient pool scheduled to undergo ultrasound testing at the wound center. Participant data will not be collected until the subject is consented. Study personnel will not have to communicate with subjects once their imaging study is complete.

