25. WAIVER OF HIPAA AUTHORIZATION

N/A

Complete this section if you seek to obtain a full waiver of HIPAA authorization to use and/or disclose protected health information.

- *Describe the risks to privacy involved in this study and explain why the study involves no more than minimal risk to privacy:*
- *Describe your plan to protect identifiers from improper use or disclosure and to destroy them at the earliest time.*
- *Indicate why it is not possible to seek subjects' authorization for use or disclosure of PHI.*
- *Indicate why it is not possible to conduct this research without use or disclosure of the PHI.*
- *Indicate if PHI will be disclosed outside NSLIJ Health System, and if so, to whom.*
Note: PHI disclosed outside NSLIJ Health System, without HIPAA authorization needs to be tracked. Please see guidance at www.nslij.com/irb for information about tracking disclosures.

In regards to the RETROSPECTIVE COHORT:

This study involves the use of data from clinical records. Patient identifiers are only needed for accurate data acquisition and tracking of outcomes. Once the data is completely abstracted, it will be de-identified. Patient privacy is protected by the anonymity of the data.

All data will be handled by only the study staff responsible for abstraction. After that it will be de-identified. Data will be stored on password protected databases housed on institutional servers. Only research personnel will have access to the database. Once accuracy of the data is verified, subjects will be assigned study IDs, and identifiers will be deleted.

Identifiers are used only during the abstraction period to access the medical records to conduct the study.

Consent to use PHI is not possible as this study only requires PHI to track and obtain additional data from Northwell EMR. Once data collection is complete, all PHI will be destroyed from the database. No PHI will be disclosed to third parties.

PHI is required to locate additional information from subject EMR.
No PHI will be disclosed to outside 3rd parties.

Complete this section if you seek to obtain a partial waiver of the patient's authorization for screening/recruitment purposes (i.e., the researcher does not have access to patient records as s/he is not part of the covered entity)

Note: Information collected through a partial waiver for recruitment cannot be shared or disclosed to any other person or entity.

- *Describe how data will be collected and used:*

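### Thirty-day readmission is read only from the Northwell EMR, so admissions that record does not show count as none, and a follow-up criterion in the 2D cohort alone could make capture unequal

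*Protocol*

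**What the plan says.** Protocol Section 10 (Endpoints): "We will review readmission rates (30 days from the day of the ultrasound". Neither Section 10 nor Section 12 says which hospitals' admissions count. Section 4 hypothesises lower readmission with 3D, also without limit. Section 8 makes this the outcome that sizes the trial: "The sample size calculation was based on the primary outcome of 30-day readmission".

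On the source of the outcome:
- **3D cohort.** Section 9: "Enrolled subject's EMR will be reviewed for 6 months after they undergo the ultrasound testing". Section 16 likewise relies on the medical record for the six months after the scan. Section 20: "Study personnel will not have to communicate with subjects once their imaging study is complete".
- **2D cohort.** Section 24 says the historical records will be reached through the EMR, and Section 25 names it: "this study only requires PHI to track and obtain additional data from Northwell EMR".

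No section provides for outside-hospital records, or says how a patient with unknown 30-day status is handled.

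On who enters, Section 7 requires of the 2D cohort only: "Subjects who were followed by the wound center team after undergoing ultrasound testing for vascular insufficiency". The 3D criteria contain nothing equivalent.

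**The concern.** With one passive data source, the absence of an admission record becomes the absence of an admission. Two separate consequences are possible.

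First, if the record misses the same share of admissions in both cohorts, both observed rates shrink. At a fixed 135 per group this would reduce power, and the result would describe a narrower event than the all-hospital readmission that the hypothesis implies.

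Second, capture may differ between cohorts. The 2D patients are selected, after the scan, for having stayed with the team whose health system supplies the outcome. The 3D patients are not, so that cohort may include people who moved their care elsewhere. If their admissions are less often visible, the 3D rate looks lower without any 3D effect. The baseline adjustment in Section 12 cannot recover admissions that were never seen.

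**Working it through.** **Inputs.** Section 8: "We assumed a readmission rate of 10% in the 2D group and a readmission rate of 2% in the 3D group" and "We would need 135 patients in each group to have 80% and a confidence level of 95% to detect this difference". I read the 80% as power and the 95% as two-sided alpha 0.05. Section 12: chi-square test. The share of admissions visible in the EMR is not given anywhere, so every capture share below is an assumption.

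**Step 1. Reproduce the plan's figure.** Unpooled normal formula: n = (1.960 + 0.842)² × [0.10 × 0.90 + 0.02 × 0.98] / (0.10 − 0.02)² = 7.849 × 0.1096 / 0.0064 = 134.4, so 135 per group. The pooled-variance version gives 138. At 135 per group, normal-approximation power is 79.4%. Exact power, from binomial enumeration of the uncorrected chi-square test, is 83.1%. The stated number is sound and leaves little spare power.

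**Step 2. Equal capture c in both cohorts.** Observed rates are 10% × c and 2% × c. This step assumes that 10% and 2% are all-hospital rates.

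| Capture c | Observed rates | Exact power | Approximate power | n per group for 80% (pooled) |
|---|---|---|---|---|
| 100% | 10.0% vs 2.0% | 83.1% | 79.4% | 138 |
| 90% | 9.0% vs 1.8% | 78.5% | 74.7% | 154 |
| 80% | 8.0% vs 1.6% | 72.7% | 69.3% | 174 |
| 70% | 7.0% vs 1.4% | 65.6% | 63.2% | 201 |

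The exact value at 90% is 78.45%, hence 78% when rounded to whole points.

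**Step 3. No 3D effect, true rate 10% in both, capture allowed to differ.** Observed rates are 10% × capture in each cohort; the test is enumerated exactly at 135 per group.

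| Capture 2D vs 3D | Observed rates | Significant, favouring 3D | Significant, favouring 2D |
|---|---|---|---|
| 100% vs 100% | 10.0% vs 10.0% | 2.5% | 2.5% |
| 80% vs 80% | 8.0% vs 8.0% | 2.5% | 2.5% |
| 90% vs 80% | 9.0% vs 8.0% | 4.8% | 1.2% |
| 90% vs 75% | 9.0% vs 7.5% | 6.5% | 0.8% |
| 90% vs 60% | 9.0% vs 6.0% | 15.1% | 0.2% |
| 75% vs 90% (reversed) | 7.5% vs 9.0% | 0.8% | 6.5% |

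Equal loss leaves the false-positive risk where it should be. Only a gap in capture moves it, and the direction follows the sign of the gap.

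**The case against.** Reading readmission from charts is an ordinary choice in a single-site, minimal-risk study, and coding rules or sensitivity analyses may sit in a statistical analysis plan that is not shown. Several stronger readings that a reader might infer also fail.

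- **That only the wound center's own record is used, so an admission to any other hospital is lost.** Section 25 names the Northwell EMR, which is a health-system record, and an outside admission noted in the chart would be visible. The exposure is to admissions that this record does not show. Whether every hospital in the system is visible is not stated.
- **That the trial is underpowered.** Step 2 needs 10% and 2% to be all-hospital rates. Section 8 gives no source. If they came from the same EMR, under-capture is already in them and no power is lost.
- **That EMR-only ascertainment in itself favours 3D.** Step 3 shows that equal capture creates no tilt.
- **That 3D capture must be lower.** The Section 7 asymmetry makes this plausible but does not show it. Section 4 expects better attendance with 3D. If that happens, outside admissions may reach 3D charts more often, and the bias would run against 3D.

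These limits stand and make the power and bias claims conditional. They do not remove two defects that the protocol itself fixes: an endpoint without a stated catchment, and a post-scan follow-up criterion in one cohort only. That criterion would be a selection problem even with perfect capture, since it may also change the true rates.

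**Conclusion.** The point holds in a conditional form. It is firm that the EMR is the only source named, that no later contact is planned, and that an admission not visible there is by default analysed as no readmission. It is also firm that post-scan follow-up by the wound center is required of the 2D cohort alone.

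The power loss (83% down to between 78% and 66% for 90% to 70% capture) is conditional on the planning rates being all-hospital rates. A false advantage for 3D (4.8% to 15% against a nominal 2.5%) is conditional on lower capture in the 3D cohort, with a true 10% rate in both. The documents settle neither condition, and the capture shares show a range, not an estimate. As written, a conclusion about readmission in general would be wider than the data can support.

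**What to change.** 1. In Sections 10 and 12, define the endpoint as an admission recorded in the Northwell EMR within 30 days of the scan, and limit the conclusion to that event.
2. State one ascertainment rule for both cohorts, covering outside admissions that are noted in the chart. Do not add patient-reported admissions in one cohort only.
3. Do not let a post-scan follow-up criterion apply to the 2D cohort alone. Replace it, in both cohorts, with a pre-scan marker of Northwell care, which the intervention cannot influence. At the least, add a sensitivity analysis restricted in both cohorts to patients with a recorded Northwell encounter in the 12 months before the scan.

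It would also help to give the source of the 10% and 2% in Section 8, so that a reader can tell whether under-capture is already included.

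The cost is a narrower claim, one extra field from charts that will be opened anyway, and a smaller sample in the sensitivity analysis.

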11. RESEARCH PROCEDURES

- *Include a detailed description of all procedures to be performed on the research subject and the schedule for each procedure.*
- *Include any screening procedures for eligibility and/or baseline diagnostic tests*
- *Include procedures being performed to monitor subjects for safety or minimize risks*
- *Include information about drug washout periods*
- *If drugs or biologics are being administered provide information on dosing and route of administration*
- *Clearly indicate which procedures are only being conducted for research purposes.*
- *If any specimens will be used for this research, explain whether they are being collected specifically for research purposes.*
- *Describe any source records that will be used to collect data about subjects*
- *Indicate the data to be collected, including long term follow-up*

The imaging device acts as an attachment to a standard ultrasound machine. The device has 2 parts. The first is a sensor which clips onto the side of the ultrasound probe. The sensor does not come into contact with the subject. This sensor then wirelessly transmits positional data to a TV box that is connected to the ultrasound's CPU. After completion of the test, this box analyzes data from the sensor and images from the ultrasound and renders a 3 dimensional model of the vasculature that was studied in the test.

The ultrasound technologist performs a standard vascular testing examination. No additional or alternative procedure and/or actions are required for the device to develop its image.

Additional data (demographics, past medical history, etc) will be garnered from the subject's EMR and stored in a password protected REDCap database. The images developed by the device will be saved on a laptop that is used exclusively for this research study.

12. STATISTICAL ANALYSIS

- *Describe how your data will be used to test the hypotheses.*
- *State clearly what variables will be tested and what statistical tests will be used.*
- *Include sample size calculations.*
- *If this is a pilot study, state which variables will be examined for hypothesis generation in later studies.*

Patients who consent to have 3D imaging of their study rendered will be shown the computer animation in addition to the handwritten sketch traditionally used by vascular surgeons. We will then compare outcomes such as 30-day re-admission rates and compliance to follow-up appointments. Ultrasound types will be grouped for analysis (lower extremity to lower extremity, upper extremity to upper extremity, etc).

The primary analysis will compare the proportion of patients readmitted within 30 days of their ultrasound among those who received the 3D ultrasound vs. those who received the 2D ultrasound using a chi-square test. We will also compare the proportion of patients who showed up for their follow-up appointment among those who received the 3D ultrasound vs. those who received the 2D ultrasound using a chi-square test. We will assess for differences in baseline characteristics and factors known to be associated with readmission and compliance with follow-up among the two groups. If warranted, we will adjust for these differences using multivariable regression models.

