19. POTENTIAL BENEFIT TO SUBJECTS

- *Explain what benefits might be derived from participation in the study, noting in particular the benefit over standard treatment (e.g. a once-a-day administration instead of four times a day, an oral formulation over an IV administration).*
- *Also state if there are no known benefits to subjects, but detail the value of knowledge to be gained*

The subject has the potential to have immediate impact from participation. They will be able to view the 3D rendering of their vasculature and their clinician will be able to highlight areas of vascular disease if any. The ability to view the disease process in a 3D model of their own vessels might increase compliance with

treatment (i.e. demonstrating stenosis of a vessel). This is a more detailed and informative picture than what is provided by standard ultrasound studies.

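### Follow-up attendance has different denominators in the two cohorts: all scanned patients for 3D, but only patients followed after the scan for 2019

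*Protocol*

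**What the plan says.** Section 10 of the protocol lists, beside 30-day readmission, "compliance to first follow-up appointment after the ultrasound of interventional cohort", to be compared with the historical cohort. Section 12 gives the analysis: "We will also compare the proportion of patients who showed up for their follow-up appointment among those who received the 3D ultrasound". The comparator is the 2D group, and the test is a chi-square. Neither section says how a patient without an appointment is handled.

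Section 7 sets different entry rules for the two cohorts.

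- **3D cohort:** adults able to consent, with a scan scheduled at the wound center and "Suspected vascular insufficiency that requires ultrasound evaluation". Nothing is required about what happens after the scan.
- **2019 cohort:** inclusion requires "Subjects who were followed by the wound center team after undergoing ultrasound testing for vascular insufficiency", and exclusion removes "Subjects who were not followed by the wound center team after undergoing ultrasound testing for vascular insufficiency".

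Section 19 allows that the scan may show nothing, since the clinician will "highlight areas of vascular disease if any". On timing, Section 9 says "Enrolled subject's EMR will be reviewed for 6 months after they undergo the ultrasound testing". That sentence is written for enrolled subjects, and no matching period is given for the 2019 charts.

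**The concern.** The hypothesis in Section 4 is about behaviour: patients who see their vessels in 3D understand their disease better and keep their appointments. Only a patient who has an appointment can show that behaviour. If the denominator is everyone scanned, the measured rate is the product of two quantities: the share given an appointment, and attendance among those given one. Scan findings and clinicians' ordering largely decide the first.

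If that share were the same in both cohorts, the main cost would be dilution. Section 7 makes it unlikely to be the same. A 3D patient with a normal scan and no follow-up ordered stays in the denominator and cannot have attended. A comparable 2019 patient would largely have been removed before any rate was calculated. The 3D rate is lowered and the 2D rate is not. A false deficit for 3D could appear, or a real benefit could be hidden. Attendance is half of the study hypothesis and has its own test, so this matters even though readmission drives the sample size.

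**Working it through.** **The plan's own figure.** Section 8 sizes the study on readmission, 10% against 2%, with 135 per group. Taking 80% as power and 95% confidence as two-sided 5%, the unpooled formula gives

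n = (1.960 + 0.842)² × (0.10 × 0.90 + 0.02 × 0.98) / 0.08² = 134.4, that is 135 per group.

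The figure reproduces (the pooled-variance version gives 138). It does not depend on the attendance denominator, and the protocol states no figure for attendance.

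**Denominators as written**

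| | 3D cohort | 2019 cohort |
|---|---|---|
| Entry (Section 7) | Suspected disease, scan scheduled | Scanned in 2019 and followed afterwards |
| Scanned, no follow-up | Stays in | Excluded |
| Denominator (Section 12) | All who received 3D | All who received 2D, after that exclusion |

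**Model.** Measured rate = b × a, where b is the share with an appointment booked and a is attendance among those booked. The protocol gives neither, so both are assumptions. I take a = 0.80 in both cohorts (no true effect) and b = 1 for 2019. The last assumption treats being followed as implying that an appointment existed.

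**Chance of a significant result.** With n = 135 per group, difference d, pooled standard error SE0 and unpooled standard error SE1, the probability is approximately Φ((d − 1.96 × SE0)/SE1).

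- b = 0.90 for 3D: rate 0.90 × 0.80 = 72%, so d = 0.08. SE0 = √(2 × 0.76 × 0.24/135) = 0.0520 and SE1 = √((0.80 × 0.20 + 0.72 × 0.28)/135) = 0.0518. Φ(−0.42) = 0.34.
- b = 0.80 for 3D: rate 0.80 × 0.80 = 64%, so d = 0.16. SE0 = √(2 × 0.72 × 0.28/135) = 0.0547 and SE1 = √((0.80 × 0.20 + 0.64 × 0.36)/135) = 0.0538. Φ(0.98) = 0.84.

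| Share of 3D patients booked | Measured 3D rate | Measured 2D rate | Falsely significant |
|---|---|---|---|
| 95% | 76% | 80% | 12% |
| 90% | 72% | 80% | 34% |
| 85% | 68% | 80% | 61% |
| 80% | 64% | 80% | 84% |

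Among booked patients only, both rates are 80% and the difference is zero.

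**If 3D truly helps.** Suppose attendance among booked patients is 90% with 3D and 80% with 2D, and all 2019 patients are booked. With 90% of 3D patients booked, the measured rates are 0.90 × 0.90 = 81% against 80%, and the benefit nearly vanishes. With 80% booked, they are 72% against 80%, and the direction reverses. The break-even share is 0.80/0.90, about 89%.

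**Equal booking.** If 90% are booked in both cohorts, the same benefit shows as 81% against 72%. The difference shrinks from 10 to 9 points, and power falls from about 64% to about 41%. Unequal booking is therefore the more serious problem.

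**The case against.** The strongest reply is that the protocol nowhere says an unbooked patient counts as non-compliant. Sections 10 and 12 both presuppose that an appointment exists, and the phrase naming those who received each type of ultrasound may only identify the comparison groups, as it does for readmission in the preceding sentence. That is a fair reading, so the point rests on the literal text and not on an express rule. But the two readings give materially different results for a tested outcome, and the text does not choose between them.

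Three stronger inferences are tempting, and the documents do not support them.

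- That both cohorts are divided by everyone scanned. Section 7 removes 2019 patients who were not followed.
- That 2D attendance is close to 100% by construction. This would need being followed to mean having attended the first appointment, and Section 7 does not define the term.
- That unbooked 3D patients are common. Section 6 describes symptomatic patients, and the remark in Section 19 concerns benefit, not booking.

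The handling of clinic-cancelled visits, deaths and inpatient stays on the appointment date is detail that a SAP would normally hold, and is not part of this point. It also stands that Section 12 makes readmission the primary analysis. The sample size is unaffected.

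**Conclusion.** The concern holds for the literal text of Section 12 read with Section 7. The 3D denominator can include patients with no appointment, while the 2019 cohort is selected on follow-up after the scan. The attendance comparison then mixes ordering of follow-up and cohort selection with patient behaviour, and this mechanism probably works against 3D.

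The size cannot be derived from the protocol. The false-significance figures of about 34% and 84% rest on assumed 80% attendance among booked patients, all 2D patients booked, and 90% or 80% of 3D patients booked. With 95% booked, the figure is about 12%. The definition should be corrected before chart abstraction. Nothing here changes the 135 per group.

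**What to change.** 1. **Sections 10 and 12:** define the outcome as attendance at the first wound center appointment booked after the index ultrasound, among patients with such an appointment. Use the same period in both cohorts, for example the 6 months already reviewed for enrolled subjects.
2. **Section 7:** replace the historical criterion of having been followed by the wound center with a rule that applies equally to both cohorts and does not depend on attendance. For example, select both on the scan and apply the requirement of a booked appointment only when this outcome is analysed. Changing Sections 10 and 12 alone would leave the 2019 cohort selected on later follow-up, and its booking rate would not be comparable.
3. **Reporting:** give the proportion with an appointment booked in each cohort beside the main result, and keep the all-patients proportion as a supporting result.

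The cost is protocol wording and two fields from the scheduling record (appointment booked, and its status). The downside is a somewhat smaller denominator that depends on booking: with 80% booked, 0.80 × 135 = 108 patients in a cohort. Booking happens after the scan and could itself differ between cohorts, so the booking rate and the all-patients rate should stand beside the main result.

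### The adjusted 30-day readmission comparison would rest on about 16 events, about 3 of them in the 3D group, too few for ordinary multivariable regression with more than a few covariates

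*Protocol*

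**What the plan says.** Protocol Section 12 compares the proportion readmitted within 30 days between the 3D and 2D groups with a chi-square test and calls this the primary analysis. Attendance at follow-up is compared in the same way. The groups are then to be checked for differences in baseline characteristics and in known predictors of both outcomes, followed by: "If warranted, we will adjust for these differences using multivariable regression models". No other method of adjustment is named.

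Section 11 shows how wide the pool of candidate covariates is: "Additional data (demographics, past medical history, etc) will be garnered from the subject's EMR". Section 12 also groups patients by the anatomical region scanned.

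Section 8 gives the planning figures: "We assumed a readmission rate of 10% in the 2D group and a readmission rate of 2% in the 3D group", and "We would need 135 patients in each group to have 80% and a confidence level of 95% to detect this difference". The controls are not concurrent: "Another 135 patients will be identified retrospectively for the historical cohort".

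**The concern.** The two cohorts are not randomised. The 3D patients are recruited prospectively and consent; the controls were scanned in 2019 and must have been followed by the wound center team after the scan (Section 7). Differences between the groups are therefore likely, and readers will lean on the adjusted readmission estimate.

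The information in a regression for a binary outcome is limited by the number of events, not the number of patients. If few readmissions are expected and very few of them fall in one group, ordinary maximum-likelihood logistic regression has two known weaknesses. The group odds ratio may have no finite estimate, and when it is finite it tends to lie too far from 1. If 3D imaging works as planned, the second error favours 3D.

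**Working it through.** **Inputs.** From Section 8: 10% (2D), 2% (3D), 135 per group, 80% (read as power), 95% confidence (read as two-sided alpha 0.05).

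**The plan's own sample size.** With unpooled variance, n = (1.960 + 0.842)² × (0.10 × 0.90 + 0.02 × 0.98) / 0.08² = 7.849 × 0.1096 / 0.0064 = 134.4, so 135 per group. The pooled formula gives 138. The stated figure is reproduced, so the rates can be taken at face value.

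**Expected events.** 2D: 135 × 0.10 = 13.5. 3D: 135 × 0.02 = 2.7. Total: 16.2, with an exact 95% range of 9 to 24.

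**No event in the 3D group.** 0.98^135 = 0.065. In that case the maximum-likelihood odds ratio is zero and its lower confidence limit is unbounded, with or without covariates. The chance of three or fewer 3D events is 71%.

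**Events per coefficient**, counting the group term: 16.2/4 = 4.1 with 3 covariates, 16.2/6 = 2.7 with 5, 16.2/9 = 1.8 with 8, 16.2/11 = 1.5 with 10.

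**Simulation.** 1,500 trials per setting, 135 per group, marginal rates 10% and 2%. Assumptions that are not in the protocol: each covariate has log odds ratio 0.4, the covariates alternate between binary (25% prevalence) and standard normal, and they are distributed alike in both groups. Maximum-likelihood (ML) means are over estimable runs only.

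| Covariates | True log OR | ML not estimable | ML mean log OR | ML exaggeration | Firth mean log OR |
|---|---|---|---|---|---|
| 0 | -1.69 | 5.5% | -1.72 | 2% | -1.66 |
| 3 | -1.71 | 6.2% | -1.75 | 2% | -1.67 |
| 5 | -1.73 | 7.6% | -1.83 | 6% | -1.73 |
| 8 | -1.77 | 8.7% | -1.93 | 9% | -1.76 |
| 10 | -1.79 | 8.8% | -2.03 | 13% | -1.77 |

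Exaggeration is the ratio of the means, for example 2.03/1.79 = 1.13. Part of it is skewness: the ML medians with 5, 8 and 10 covariates are -1.79, -1.84 and -2.00, which are 3%, 4% and 12% too far from zero. Against that, the non-estimable runs are left out, which understates the problem. Firth's method gave an estimate in every run with up to 8 covariates and in 1,499 of 1,500 with 10.

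A second simulation with normal covariates only (log odds ratio 0.5) found 5.3%, 5.9%, 6.6% and 6.6% of fits unusable with 1, 2, 4 and 8 covariates. Each figure equalled the share of trials with no 3D event.

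**The case against.** The strongest objection is that the primary result is not at risk. That stands: the primary analysis is the unadjusted chi-square test, which no number of covariates can overfit. A reader might infer that the trial's main result is unreliable on this account; Section 12 does not support that. The regression is conditional on differences being found.

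Second, the harm depends on a covariate count that the protocol does not state, and the choice of covariates is commonly left to a statistical analysis plan. This also stands. Adjustment may involve only one or two variables, and the exaggeration is then small. The absence of a list is not the point made here.

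Third, multivariable regression is a family of methods. The protocol does not commit to ordinary maximum likelihood or Wald tests, and Firth's method belongs to the same family. That is fair, and it is why the fix sharpens Section 12 rather than overturning it.

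Fourth, most of the non-estimability comes from the empty 3D cell, not from adjustment: 5.5% with no covariates against 8.7% with eight. This is correct.

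Fifth, a reader might infer that regression wastes power and should give way to propensity weighting. The calculations do not show that. The loss is mainly a feature of Wald tests. With eight covariates and no imbalance, power was 78% for Wald, 87.6% for the likelihood ratio and 86.2% for an overlap-weighted risk difference. With a 0.2 SD imbalance in each covariate it was 41.1% for the likelihood ratio and 42.9% for overlap weighting. Weighting also changes the quantity estimated, and with no 3D events its interval is unreliable too.

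**Conclusion.** The point holds in a limited form. The protocol's own planning rates imply about 16 readmissions, about 3 of them in the 3D group. For the adjusted readmission comparison, the method named, in its ordinary form, fits that count badly: about 5-9% of analyses without a finite odds ratio, and a 3D effect exaggerated by roughly 5-13% on the log-odds scale with five or more covariates.

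The event count rests on Section 8's rates. If both groups had 10% there would be 27 events; if both had 2%, about 5. The exaggeration rests on the assumed covariate effects and number. The conclusion does not extend to the chi-square test, to power, or to follow-up attendance, for which the protocol gives no expected rate. A statistical analysis plan that is not shown may already restrict the model. This is worth changing because it costs little, not because it invalidates the design.

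**What to change.** In Section 12, state that:

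- the adjusted comparison of 30-day readmission uses Firth-penalised logistic regression, with profile penalised-likelihood confidence intervals and tests in place of Wald ones;
- it includes a short list of covariates measured before the scan and available in the EMR, fixed before outcomes are compared. Penalisation removes most of the bias but does not create information, so the list should stay short;
- ordinary multivariable regression is kept for follow-up attendance.

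An overlap-weighted risk difference from a propensity score may be added as a sensitivity analysis, with a note that it describes patients who could have been in either cohort.

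The cost is wording only; patients and data source are unchanged. The penalised odds ratio is slightly shrunk towards no effect (for example -1.67 against a true -1.71 with three covariates), and the method is a little less familiar to readers. The text should claim a finite, nearly unbiased estimate, not more power.
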